7.5 Participant Investigation Completion and Premature Discontinuation

Following the index procedure, every participant into whom the Pristine™ Catheter was placed should remain in the study until completion of the required follow-up period or until day of remove of the Pristine™ Catheter. The follow-up period for this clinical investigation is 12 months (365 ± 30 days) for participants who had the Pristine™ Catheter successfully placed. An enrolled participant is considered to have completed the study if the participant has completed the formal follow-up period associated with this clinical investigation through the 12-Month follow-up as described in the Schedule of Activities (Section 1.3).

Upon investigation completion or premature discontinuation (in the situations where applicable), the participant's continued care should be administered per SOC at the discretion of the PI and / or their primary care physician.

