3.2 Secondary Endpoints

The following secondary endpoints will be evaluated using descriptive statistics to provide further information related to the safety and performance of the Pristine™ Long-Term Hemodialysis Catheter. All secondary endpoints will be summarized with descriptive statistics.

- *Rate of freedom from catheter-related bloodstream infection (CRBSI)*, defined by 2019 KDOQI Guidelines for CRBSI through 1-month, 3-months, 6-months, and 12 months post-index procedure.

- *Rate of freedom from Device and/or Procedure-related adverse events*, at 1-month, 3-months, 6-months, and 12 months post-index procedure.
- *Rate of Technical Success*, defined as the successful placement of the Pristine™ Long-Term Hemodialysis Catheter, as assessed by the Investigator during the Index Procedure.
- *Overall Participant Survival Rate* at 1-month, 3-months, 6-months, and 12 months post-index procedure, defined as the proportion of participants that have not died from any catheter related complication.
- *Overall Catheter Survival Rate* at 1-month, 3-months, 6-months, and 12 months post-index procedure, defined as the proportion of Pristine™ Catheters that have not been removed for any cause.
- *Overall Patency Rate*, at 1-month, 3-month, 6-months, and 12-months post-index procedure, defined as the Pristine™ catheter having the ability to achieve a mean dialysis blood flow of $\geq 300\text{mL/min}$ without need for additional interventions.^{5,6}

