The primary endpoint for this study is a combined complication rate of non-infectious and infectious complications. Non-infectious complications are defined as, complications due to any noninfectious cause (thrombosis of the access, fibrin material within or around a catheter, catheter migration, central vein stenosis or thrombosis) requiring a revision procedure to maintain patency or improve access performance (i.e., thrombolysis, angioplasty, or surgical correction) in an inpatient or outpatient setting or removal or abandonment with creation of a new access that was not due to an access-related infection). This definition of non-infectious provides the clinically relevant point of re-intervention. Thrombosis, fibrin material, and catheter migration are all common events for tunneled catheters. When these events start to disrupt dialysis treatment, they require re-intervention thus putting more burden on the patient and healthcare system. The other part is infectious complications defined as, complications due to any documented diagnosis of access infection requiring medical intervention (managed in an outpatient or inpatient setting) or sepsis as diagnosis in the hospitalization file whether access related or not. Infection rate for catheters is arguably the most crucial reported value being the main cause of catheter related deaths. The infectious complications defined include exit site infections and all blood stream infections causing sepsis.

Showing a statistically significant difference by our powered primary endpoint against the performance goal will attest to the performance, safety, and clinical benefits of the Pristine™ Catheter.

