7.2.1 Clinical Procedure

After the PI, or authorized designee(s), has determined that the participant is eligible for participation based on the criteria listed in Section 5.1 and 5.2, the participant may be enrolled and undergo the Pristine™ Catheter placement procedure. Examinations, evaluations, procedural preparation, angiography, treatment, and hospital / facility discharge procedures will be conducted per the investigational site's SOC.

The placement of the Pristine™ Catheter, will be per the investigational site's SOC and must adhere to the device IFU. Operators of the Pristine™ Catheter must be approved by the Sponsor as an operator in writing before conducting an index procedure on enrolled participants (refer also to Section 13.3). For detailed information on device use and procedural medication recommendations, reference the IFU.

Enrolled participants will continue clinical participation through the 12-month follow-up period. Participants into whom the Pristine™ Catheter was not introduced should be treated per SOC and the reason documented on the appropriate eCRF. Participation for these participants will end at time of the index procedure.

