7.4 Participant Follow-Up

7.4.1 Follow-Up Intervals and Methods

Enrolled participants will have follow-up visits at 1-month, 3 months, 6-months, and 12-months via either in person visit or telephone call. For participants into whom the Pristine™ Catheter was introduced during the index procedure, but procedure success was not achieved, only the procedure eCRF will be collected and limited to the collection of safety events and interventions for up to 30 days.

Follow-up windows will be calculated from the index procedure date. Refer to Section 1.2 for an overview of follow-up window time frames and requirements for each visit. The

following data will be collected and documented on the appropriate eCRF for each follow-up unless otherwise specified for treated participants:

- Hemodialysis Catheter Assessment:
 - Document how the participant has been receiving hemodialysis and document the date of the participant's last HD session.
- Dialysis Session Blood Flow Rate:
 - If dialyzing through the Pristine™ Catheter, document the reported dialysis sessions and details such as date of dialysis session, average blood flow rate, number of line reversals, and length of dialysis session.
- If Needed:
 - Documentation of any protocol deviations that have occurred since the last follow-up.
 - Documentation of occurrence and / or status of AEs since the last follow up (refer to Section 9).
 - Any catheter reinterventions the participant has undergone since the prior follow-up.

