8 PARTICIPANT DISCONTINUATION/WITHDRAWAL

8.1 Discontinuation/Withdrawal

- A participant may withdraw from the study at any time at his/her own request (Withdrawal of Consent) or may be withdrawn at any time at the discretion of the investigator (Investigator's Decision) or sponsor (Sponsor's Decision) for safety, behavioral, compliance, or administrative reasons.
- Once a participant discontinues from the study, no further data will be collected.
- If the participant withdraws consent for disclosure of future information, the sponsor may retain and continue to use any data collected before such a withdrawal of consent.
- If a participant withdraws from the study, the reason for withdrawal must be documented.

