9 ADVERSE EVENTS AND DEVICE DEFICIENCIES

9.1 Definitions of Events

9.1.1 Adverse Events (AEs)

An AE is defined as any untoward medical occurrence, unintended disease or injury, or untoward clinical signs (including abnormal laboratory findings) in participants, users or other persons, whether or not related to study device [ISO14155:2020(E)].

Pre-existing conditions should be considered as part of the participant's medical history and should not be reported as an AE unless there is a substantial increase in severity or frequency of the condition. Likewise, planned hospital visits and/or hospital stays should not be considered as adverse events. Exacerbation of an existing condition should be reported as an AE if the event meets the protocol definition of an AE.

The clinical course of the event will be followed according to accepted standards of medical practice until the event resolves, stabilizes, or in the opinion of the Investigator, is no longer considered clinically significant. The Investigator must supply the Sponsor with information concerning the follow up and/or resolution of the AE.

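### Protocol 7.5 ends participation at catheter removal, contradicting 4.1 and 7.2.1, so later catheter-related deaths may be missed and 12-month participant survival biased in the device's favour

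*Protocol*

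**What the plan says.** Protocol 7.5 states that a participant in whom the catheter was placed "should remain in the study until completion of the required follow-up period or until day of remove of the Pristine™ Catheter". The same section sets the planned length: "The follow-up period for this clinical investigation is 12 months (365 ± 30 days) for participants who had the Pristine™ Catheter successfully placed". It makes no exception by reason for removal.

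Other sections describe follow-up that does not stop at removal:

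- Protocol 7.2.1: "Enrolled participants will continue clinical participation through the 12-month follow-up period". Protocol 4.1 likewise schedules 1-, 3-, 6- and 12-month follow-up for everyone enrolled.
- Protocol 7.4.1 has the site at each visit "Document how the participant has been receiving hemodialysis", and asks for session details only when dialysis runs through the study catheter.
- Protocol 9.1.1 on adverse events: "The clinical course of the event will be followed according to accepted standards of medical practice until the event resolves", or until it stabilises or loses clinical significance.

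Protocol 8.1 adds: "Once a participant discontinues from the study, no further data will be collected". SAP section 7 collects adverse events up to the last follow-up visit or early termination.

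The affected endpoint is Overall Participant Survival at 1, 3, 6 and 12 months, "defined as the proportion of participants that have not died from any catheter related complication" (Protocol 3.2). SAP 5.3.4 makes a participant non-evaluable (binary analysis) or censored (Kaplan-Meier) after study discontinuation, or after removal for transplant, transfer to AVF/AVG, peritoneal dialysis, withdrawal of care or other reasons. Removal for infection or catheter dysfunction is not on that list. Anyone left over is a success in the binary analysis, and event-free to the visit day in the Kaplan-Meier analysis.

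**The concern.** Protocol 4.2 gives the reason this exit matters: "Infection rate for catheters is arguably the most crucial reported value being the main cause of catheter related deaths". If an infected catheter is removed and the participant leaves the study that day, observation stops because of the complication whose fatal outcome the endpoint is meant to count. The loss is therefore informative, and it runs in one direction.

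The contradiction also means that sites can reasonably act differently. One reading 7.5 closes the participant out at removal; one reading 4.1 or 7.2.1 keeps calling to month 12. Completeness of vital status would then depend on the site.

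Long-term safety is the stated secondary objective, and Protocol section 3 says the results are meant for the device's labeling. A survival figure that cannot register deaths after removal would be read as stronger evidence than it is.

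**Working it through.** **1. The plan's own figures.** No stated figure covers this endpoint. The sample size concerns only the 3-month primary endpoint, and it reproduces. 12765/90 = 141.8, so 142 participants; 12765 × 0.85 = 10850 patient-days after 15% attrition. An exact one-sided Poisson test at 0.025 then gives 80.3% power for 31.5 against 36.5 per 1000 days, and 85.5% for 26.5 against 31.5. None of this depends on what happens after removal.

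**2. What status does a participant have after removal?** Protocol 4.4 and 7.5 define completion as finishing 12-month follow-up, so exit at removal is not completion. Appendix A, under access censoring events, gives the reasons for premature discontinuation as withdrawn consent, withdrawal by the investigator, loss to follow-up and death. Removal is not among them. The status is undefined, and SAP 5.3.4 turns on it.

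**3. What SAP 5.3.4 does with a participant whose catheter is removed for infection or dysfunction and who later dies of it, the death being unobserved.**

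- Exit coded as discontinuation: non-evaluable for visits whose window opens later, and censored at exit. The death is in neither numerator nor denominator.
- Exit not so coded: a success by default, and event-free to the visit day, although under 7.5 no visit takes place.

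Neither path counts the death.

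**4. Which other endpoints are affected?** Freedom from CRBSI (SAP 5.3.1) and from device- or procedure-related adverse events (SAP 5.3.2) set failure at the event date. A qualifying device-related infection that led to removal has already been counted, so that participant adds no bias. Removal for infection or dysfunction is itself a failure for catheter survival (SAP 5.3.5). What may be lost is later adverse events, adverse-event totals, and first related events arising after a removal for another reason.

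**5. Size.** The smallest case needs only N = 142, all evaluable, and no other catheter-related death. With one death after removal, full follow-up gives 141/142 = 99.3% (exact 95% CI 96.1 to 100.0). If it is missed and scored a success, the report is 142/142 = 100% (lower limit 97.4).

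For a range, the inputs must be assumed, since the documents give none. Assume that 10 to 30% have removal for infection or dysfunction, that 5 to 20% of those later die of a catheter-related complication, that all these deaths are missed, and that there are no others:

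- Low: 142 × 0.10 ≈ 14 removals; 14 × 0.05 = 0.7, about 1 death. Overstatement if scored as success: 1/142 = 0.7 points.
- High: 142 × 0.30 ≈ 43 removals; 43 × 0.20 = 8.6, about 9 deaths. Full follow-up gives 133/142 = 93.7% (88.3 to 97.1). Overstatement: 9/142 = 6.3 points.
- If exits are non-evaluable instead, the report is 128/128 (lower limit 97.2%) to 99/99 (lower limit 96.3%), still 100%.

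This range illustrates sensitivity to the assumptions; it is not an estimate.

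**The case against.** The strongest reply is that Protocol 7.5 is one clause among several and that the others keep the information flowing. Much of that stands, and it rules out several stronger readings.

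- A reader might infer that deaths after removal are never observed. The documents do not support that. An infection open at removal is to be followed under 9.1.1, and the investigator must report its outcome to the sponsor. Protocol 9.4 requires any death to be reported within one business day of awareness, with no condition that the catheter be in place. But 9.1.1 schedules no contact and does not cover a problem that first appears after removal, and 9.4 governs only deaths the site already knows of.
- A reader might infer that 8.1 forbids data collection after removal. It deals with withdrawal by the participant, investigator or sponsor, and nothing classes removal as such a withdrawal. This is a gap, not a prohibition.
- A reader might infer that the safety endpoints in general miss the infections behind removals. Step 4 of the working shows that they do not.
- A reader might take the feasibility study's 9 deaths among 45 participants as a guide to the number missed. None was reported as related to the device or procedure, and this endpoint counts only catheter-related deaths. The 6 device-related infections are not reported as removals.
- The removal list in SAP 5.3.4 recurs throughout SAP 5.3, so omitting infection there may be shared text rather than a decision about survival. The dialysis-route question in 7.4.1 also fits a participant whose catheter is in place but unused. Both are supporting evidence only.

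Limiting follow-up to the time the device is in place can be a legitimate design. It does not suit an endpoint that counts deaths to 12 months, and it is not what 4.1 and 7.2.1 describe.

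**Conclusion.** The point holds as an unresolved contradiction with a one-sided consequence. Protocol 7.5 cannot be reconciled with 4.1 and 7.2.1, and fits poorly with 7.4.1 and 9.1.1. A site that follows it has no scheduled contact through which to learn of a catheter-related death after removal for infection or dysfunction. SAP 5.3.4 then excludes, censors or credits the participant, so 12-month participant survival can be biased in the device's favour. Later adverse events and their totals are also exposed.

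The number of deaths missed is unknown and may be zero. It depends on the removal rate, on mortality after removal, and on how much 9.1.1 and 9.4 recover in practice. Because catheter-related deaths may be few, even one missed death can decide whether the report reads 100%. The endpoint is secondary and descriptive, so the primary test, sample size and power are unaffected.

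**What to change.** **Protocol.** Reconcile 7.5 with 4.1, 7.2.1, 7.4.1 and 9.1.1. State that removal ends catheter exposure (patency, catheter survival, days counted for complications) but not participation, and is not a discontinuation under 8.1. Collect vital status and adverse events at the remaining scheduled contacts, and follow the event that led to removal as 9.1.1 already requires.

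**SAP.** Amend 5.3.4, binary and Kaplan-Meier, so that removal for any reason neither makes a participant non-evaluable or censored, nor a default success, while vital status is known. Censor at last known contact. A Protocol change alone would not be enough: the current list would still keep deaths after removal for transplant, AVF/AVG, peritoneal dialysis, withdrawal of care or other reasons out of the endpoint. Check that the exposure rule in 5.2.1, which uses the same list of removal reasons, agrees with the clarified end of catheter exposure.

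**Cost.** Amendment wording, a small SAP revision, and a few extra calls to participants who no longer have the catheter. The contacts are already scheduled for all enrolled participants and may be by telephone. Sample size does not change.

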8 PARTICIPANT DISCONTINUATION/WITHDRAWAL

8.1 Discontinuation/Withdrawal

- A participant may withdraw from the study at any time at his/her own request (Withdrawal of Consent) or may be withdrawn at any time at the discretion of the investigator (Investigator's Decision) or sponsor (Sponsor's Decision) for safety, behavioral, compliance, or administrative reasons.
- Once a participant discontinues from the study, no further data will be collected.
- If the participant withdraws consent for disclosure of future information, the sponsor may retain and continue to use any data collected before such a withdrawal of consent.
- If a participant withdraws from the study, the reason for withdrawal must be documented.

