10.2 Sample Size Considerations

The primary objective of the study is to show the overall complication rate for Pristine is non-inferior to the performance goal at 3 months. If successful, the next step is to show superiority of Pristine at 3 months.

Based on hypothesis test of Non-inferiority

- Assumptions:
 - The complication rate of our performance goal is estimated at 31.5 events per 1000 patient days with a 90 days follow-up based on DOPPS study data. The complication rate for Pristine is expected to be similar.
 - The performance goal is set at 36.5 events per 1000 days using a 5 events per 1000 days non-inferiority margin;
 - The attrition through 90 days is assumed to be 15%
 - The Type 1 error is 0.025 (one-sided).

- The Type 2 error is 0.2.
- Sample Size:
 - Total required exposure is 12765 patient days which translates to 142 participants with average exposure of 90 days (PASS 2019).

Based on hypothesis test of Superiority

- Assumptions:
 - The complication rate of our performance goal is estimated at 31.5 events per 1000 patient days with a 90 days follow-up based on literature review, which is set as the performance goal.
 - The complication rate for the Pristine™ Catheter is assumed to be 26.5 events per 1000 patient days.
 - The attrition through 90 days is assumed to be 15%
 - The Type 1 error is 0.025 (one-sided).
- Sample Size:
 - Total exposure of 12765 patient days (which translates to 142 participants with average exposure of 90 days) will provide 85% power of the test (PASS 2019).

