10.4 General Considerations

10.4.1 Handling of Missing Data

Study endpoints may have missing data due to a participant's withdrawal of consent, the withdrawal of a participant by the PI, a participant loss to follow-up and the death of a participant. Data may also be missing from investigation endpoints due to deviations and / or missing data collection. It is important to minimize missing data by all means and to always record the reason for omission.

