## 2.3 Randomization and Blinding

Randomization and blinding are not applicable for this study.

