#### Infectious Complications

Complications due to any documented diagnosis of access infection requiring medical intervention (managed in an outpatient or inpatient setting) or sepsis as diagnosis in the hospitalization file whether access related or not.

Subject will be considered as having an infectious complication and will be counted as an event if the subject has experienced a device-related infection prior to the subject's end day of investigation period:

- **AE CRF Page:** Start Date of AE ≤ End Day of Investigation period **AND** Relationship to study Device: Equals 'Related' or 'Likely Related' **AND** Was event infectious: Equals Yes; subject will be considered as a failure at AE start date

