#### Non-infectious complications

Complication due to any noninfectious cause (thrombosis of the access, fibrin material within or around a catheter, catheter migration, central vein stenosis or thrombosis) requiring a revision procedure to maintain patency or improve access performance (i.e., thrombolysis, angioplasty, or surgical correction) in an inpatient or outpatient setting or removal or abandonment with creation of a new access that was not due to an access-related infection.

Subject will be considered as having a non-infectious complication and will be counted as an event if the subject has experienced a device-related non-infectious AE resulting in a re-intervention prior to the subject's end day of investigation period:

- **AE CRF Page:** Start Date of AE  $\leq$  End Day of Investigation period **AND** Relationship to study Device: Equals 'Related' or 'Likely Related' **AND** Was event infectious: Equals No **AND** Did AE Result in a Catheter Re-Intervention: Equals Yes; subject will be considered as a failure at AE start date

For each subject, the number of complications through the investigational duration is estimated as:

$$((\text{Number of observed infectious complications} + \text{Number of observed non-infectious complications}) * 1000) / \text{Length of investigation duration (Days)}$$

Length of investigation duration (Days) is from the date of index procedure to the end day of each subject's investigation period (End day of investigation period – Date of index procedure + 1); the end day of investigational period will be the earliest occurrence date of the following three events:

- If a subject's Pristine™ Catheter is removed due to Kidney Transplant, Transferred to AVG/AVF, Peritoneal Dialysis, Withdrawal of Care, or Other reasons, then the date of removal will be used to calculate the length of investigation duration. That is:
  - **Hemodialysis Catheter Re-Interventions CRF page:** Catheter removal Equals Yes **AND** Reason for catheter removal Equals: Kidney Transplant, Transferred to AVG/AVF, Peritoneal Dialysis, Withdrawal of Care, or Other; date of re-intervention is used in the estimation of investigation duration

$$\text{Length of investigation duration (Days)} = \text{Removal date} - \text{date of index procedure} + 1$$

- If a subject discontinues early, then the discontinuation date will be used to calculate the length of investigation duration.
 

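### No data are collected after an investigator or sponsor withdraws a participant, so the primary complication rate can be biased low if those participants would have fared worse than the ones who stay

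*Protocol*

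**What the plan says.** Protocol 8.1 allows withdrawal at the participant's request or at the discretion of the investigator or sponsor, in the latter cases "for safety, behavioral, compliance, or administrative reasons". The next bullet reads: "Once a participant discontinues from the study, no further data will be collected". A separate bullet deals with withdrawn consent for disclosure, so the stop on data is not confined to participants who refuse further use of their data.

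SAP 5.2.1 carries this into the primary endpoint. On exposure: "If a subject discontinues early, then the discontinuation date will be used to calculate the length of investigation duration". On events, an adverse event counts only if "Start Date of AE ≤ End Day of Investigation period". Events and days before withdrawal stay in the rate; everything later is absent from both numerator and denominator. Protocol Appendix A likewise lists withdrawal by the investigator as an access censoring event.

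The design is open: "Randomization and blinding are not applicable for this study" (SAP 2.3). Under Protocol 9.4, device-related events reach the sponsor within one working day. Protocol 10.4.1 names investigator withdrawal as a source of missing data, but its instruction is only this: "It is important to minimize missing data by all means and to always record the reason for omission". The one sensitivity analysis for the primary endpoint is per-protocol (Protocol 10.5, SAP 5.2.1 and 5.2.2).

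**The concern.** SAP 5.2.2 estimates a single rate from an intercept-only Poisson model. That is sound under early exit only if the days not observed would have had the same complication rate as the days observed. Withdrawals decided for safety or compliance are the ones where this is least secure. The people deciding know how the participant is doing, and no control arm shares any resulting bias.

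At stake is the comparison with the performance goal. If the lost days carry above-average risk, the observed rate falls below the rate that full follow-up would have shown, and the chance of a false non-inferiority claim exceeds 2.5%. The 15% attrition allowance does not help, because it replaces lost patient-days and takes no account of who is lost. The missing events cannot be reconstructed at analysis.

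**Working it through.** **1. The plan's own figure.** Protocol 10.2 and SAP 2.4 give: "The performance goal is set at 36.5 events per 1000 days using a 5 events per 1000 days non-inferiority margin". The other inputs are an expected rate of 31.5, one-sided alpha 0.025, type 2 error 0.2, attrition 15% through 90 days, 12,765 patient-days and 142 participants.

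- Normal approximation: T = (1.96·√0.0365 + 0.842·√0.0315)² / 0.005² ≈ 10,976 days. Then 10,976/0.85 ≈ 12,913 days, and 12,913/90 = 143.5, so 144 participants. This is close to the stated figures.
- Exact Poisson at 12,765 × 0.85 ≈ 10,850 days: reject if events ≤ 357; alpha 0.02497, power 80.3%.

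The stated 12,765 days therefore already contain the 15% allowance, and that allowance covers volume of exposure only.

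**2. Effect of informative withdrawal.** These inputs are assumptions, not document figures:

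- The full-follow-up rate is exactly 36.5 per 1000 days, the boundary of the null hypothesis.
- Full exposure is 142 × 90 = 12,780 days, so expected events are 0.0365 × 12,780 = 466.5.
- n participants are withdrawn by the investigator or sponsor, each losing 45 days.
- Their rate in the lost days is k times 36.5 per 1000.

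Formulas:

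- Observed days = 12,780 − 45n
- Expected observed events = 466.5 − 45n × k × 0.0365
- False-pass probability = P(Poisson(expected observed events) ≤ c), where c is the largest count with P(Poisson(0.0365 × observed days) ≤ c) < 0.025

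Worked case, n = 7 and k = 2: observed days = 12,780 − 315 = 12,465. Lost events = 315 × 2 × 0.0365 = 23.0, so expected observed events = 443.5. The observed rate is 443.5/12,465 = 35.6 per 1000. Here c = 413 and the false-pass probability is 7.6%. With k = 1.5 and 3 the observed rates are 36.0 and 34.7.

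| Withdrawals (n) | k = 1.5 | k = 2 | k = 3 |
|---|---|---|---|
| 2 | 2.7% | 3.2% | 4.4% |
| 5 | 3.7% | 5.6% | 11% |
| 7 | 4.5% | 7.6% | 19% |
| 10 | 5.5% | 11% | 34% |

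With k = 1 the probability stays between 2.2% and 2.5% for every n, so the inflation comes entirely from the difference in risk. Starting from 85% of the exposure (10,863 days) changes little: n = 7 gives 4.5%, 8.0% and 21%.

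**3. Do other sections close the gap?**

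- Protocol 7.5 says participants should stay until completion or catheter removal. That discourages withdrawal but does not govern what follows it.
- Protocol 8.1 requires the reason to be documented, and SAP 6.1 tabulates discontinuations by reason. This describes the loss without recovering events.
- Protocol 9.1.1 says of an adverse event: "The clinical course of the event will be followed according to accepted standards of medical practice until the event resolves, stabilizes". This covers events already begun and, read literally, conflicts with 8.1.
- The per-protocol analysis excludes participants with major deviations and restores no post-withdrawal data.

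None of these captures a new complication after withdrawal.

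**The case against.** A reader might infer that the primary rate will be biased low, or that up to 15% of participants will be lost in this way. The documents support neither. They contain no data on risk after withdrawal. The permitted reasons include behavioral and administrative ones with no evident link to complications, and a non-compliant participant could have a higher or a lower recorded rate. The 15% is a planning assumption for all attrition, with no breakdown, and Appendix A lists several other censoring routes: transplant, transfer to another form of access or dialysis, withdrawn consent, loss to follow-up and death.

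The upper end of the table is also extreme. At k = 3, a withdrawn participant would have about 45 × 3 × 0.0365 = 4.9 qualifying complications in 45 days. With only 2 such withdrawals the error stays close to nominal.

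Finally, the calculation sits at the boundary rate of 36.5, and the feasibility study in Protocol 2.1 suggests something far lower. Nine infections plus about 4 patency losses (9.1% of 44) over at most 45 × 180 = 8,100 days is about 1.6 per 1000. Halving the exposure for deaths and dropout gives about 3. The definitions differ, so this is only indicative, but near such rates a shift of 0.5 to 2 per 1000 would not change the result.

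All of this stands as a limit on size and likelihood. It does not answer the structural point: a rule that discards obtainable primary-endpoint data after a discretionary decision, with no analysis to test its effect.

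**Conclusion.** The concern holds in conditional form. Protocol 8.1 and SAP 5.2.1 together remove all follow-up after investigator- or sponsor-decided withdrawal. The primary rate can then be biased low if, and only if, those participants' later complication rate would have exceeded that of participants who remain. The size cannot be determined from the documents. Under the stated assumptions, type I error at the boundary runs from 2.7% (2 withdrawals, k = 1.5) to 34% (10 withdrawals, k = 3). Few withdrawals, risk-neutral reasons or a true rate well below 36.5 would make it immaterial. The change should be made because it is cheap and must be in place before withdrawals occur, not because bias has been shown.

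**What to change.** - **Protocol 8.1:** limit the no-further-data rule to participants who withdraw consent for further data collection. For investigator- or sponsor-decided withdrawals who still consent, continue the existing dialysis-center contact for complications, re-interventions and vital status through the 3-month visit.
- **Protocol 8.1 and 9.1.1:** reconcile the stop on data collection with the requirement to follow adverse events already begun.
- **SAP 5.2.1:** for these participants, end exposure at the last date of known status, within the existing catheter-removal and day-105 rules, and count events to that date.
- **SAP 5.2.2:** prespecify a sensitivity analysis, for example a tipping point on the post-withdrawal rate, with a listing of these withdrawals by reason and prior complications.

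The cost is protocol and consent wording, a short SAP addition, and a few extra calls of a kind already in the schedule (Protocol 6 and 7 provide for telephone follow-up with the participant and dialysis center).
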